10.1.1.5. Audits and Inspections

The study may be audited according to the Sponsor's quality assurance inspection program. The purpose of the audit is to determine whether or not the study is being conducted and monitored in compliance with study protocol and ICH-GCP guideline. Audit visit(s) will be arranged in advance with site personnel at a mutually acceptable time.

The Investigator should understand that source documents for this study should be made available to appropriately qualified personnel from the Sponsor quality assurance or its designees or to regulatory authority inspectors after appropriate notification. The verification of the eCRF data must be by direct inspection of source documents. These audits or inspections may take place at any time, during or after the study, and are based on the national regulations, as well as ICH-GCP guidelines.

10.1.1.6. Data Quality Assurance

All subject data relating to the study will be recorded on printed or electronic case report form (eCRF) unless transmitted to the Sponsor or designee electronically (e.g., laboratory data). The investigator is responsible for verifying that data entries are accurate and correct by physically or electronically signing the eCRF.

The investigator must maintain accurate documentation (source data) that supports the information entered in the eCRF.

The investigator must permit study-related monitoring, audits, IRB/IEC review, and regulatory agency inspections and provide direct access to source data documents.

Monitoring details describing strategy (e.g., risk-based initiatives in operations and quality such as Risk Management and Mitigation Strategies and Analytical Risk-Based Monitoring), methods, responsibilities, and requirements, including handling of noncompliance issues and monitoring techniques (central, remote, or on-site monitoring), are provided in the Monitoring Plan.

The sponsor is responsible for the data management of this study, including quality-checking of the data.

The investigator assumes accountability for actions delegated to other individuals (e.g., contract research organizations).

Study monitors will perform ongoing source data verification to confirm that data entered into the eCRF by authorized site personnel are accurate, complete, and verifiable from source documents; that the safety and rights of subjects are being protected; and that the study is being conducted in accordance with the currently approved protocol and any other study agreements, ICH GCP, and all applicable regulatory requirements.

Records and documents, including signed ICFs, pertaining to the conduct of this study must be retained by the investigator per ICH GCP* and local regulations or institutional policies.

No records may be destroyed during the retention period without the written approval of the Sponsor. No records may be transferred to another location or party without written notification to the Sponsor.

* As per ICH E6 (R2), paragraph 1.65, computerized systems used to record data, should be validated and compliant with 21CFR part 11 (EudraLex4 annex 11 in EU). Data integrity should be maintained throughout the study (as per ICH E6 (R2) 5.5.3, Good Documentation Practiced as per ICH E6 (R2) 4.9.0 (ALCOA++).

10.1.2. Study Monitoring

The Monitor has the responsibility to familiarize the Investigator(s) and the entire center staff involved in the study with all study procedures including the administration of investigational product. The Monitor will monitor the study conduct, proper eCRF and source documentation completion and retention, and accurate investigational product accountability. To this end, the Monitor will visit the clinical site at suitable intervals and be in frequent contact through verbal and written communication. It is essential that the Study Monitor has access to all documents (related to the study and the individual participants) at any time these are requested. In turn, the Monitor will adhere to all requirements for subject confidentiality as outlined in the ICF. The Investigator and Investigator's staff will be expected to cooperate with the Study Monitor, permit the monitor, the IEC/IRB, the Sponsor's internal auditors, and representatives from regulatory authorities direct access to all study-related documents and pertinent hospital or medical records for confirmation of data contained within the eCRFs to be available during a portion of the monitoring visit to answer questions, and to provide any missing information.

10.1.3. Study Documentation

Study documentation will follow Good Documentation Practice as per ICH E6 (R2) 4.9.

Study documents will include but not be limited to the following:

- Signed ICFs
- Source documents (e.g., subject files, medical notes, study worksheets)
- Investigator copies of the eCRFs and SAE reports
- Investigator site file and contents
- Study Manuals (including laboratory manual, pharmacy manuals and reference manual)
- Investigator meeting binder and or other training materials

Upon completion of the study, the study monitor will arrange for a final review of the study files after which the files should be secured for the appropriate period.

10.1.3.1. Change in Protocol

There will be no alterations in the protocol without agreement between the Sponsor and the Investigator.

There will be no alterations in the protocol affecting subject safety without the express written approval of the Sponsor, Investigator, and the IEC/IRBs.

All protocol amendments must be submitted to the EC/IRBs and regulatory authorities if required by local law. Protocol modifications that affect subject safety, the investigational scope, or the scientific quality of the study must be approved by the IEC/IRBs before implementation of such modifications to the conduct of the study. If required by local law, such modifications must also be approved by the appropriate regulatory agency before implementation. However, the Sponsor may, at any time, amend this protocol to eliminate an apparent immediate hazard to a subject. In this case, the appropriate regulatory authorities will be notified subsequent to the modification.

10.1.3.2. Site Initiation Visit/Investigator Meeting

Prior to the start of the clinical study, the representative(s) of the Sponsor will meet with the Investigator and appropriate clinical staff to familiarize the Investigator and clinical staff with the clinical protocol and the materials necessary for conducting the clinical study.

10.1.3.3. Source Document

The Investigator will permit study-related monitoring, audits by or on behalf of the Sponsor, IRB/IEC review and regulatory inspections providing direct access to source data documents. Source documents are original records in which raw data are first recorded. These may be office/clinic/hospital records, charts, diaries, ultrasound images, and laboratory results, ECG printouts, pharmacy records, care records, completed scales for each study participant and/or worksheets provided by the Sponsor. Source documents should be kept in a secure and limited access area. All source documents should be accurate, clear, unambiguous, permanent and capable of being audited. They should be made using a permanent form of recording (ink, typing, printing, optical disc, etc.). They should not be obscured by correcting fluid or have temporary attachments (such as removable self-stick notes). Source documents that are computer generated and stored electronically must be printed, signed and dated by the Investigator.

Source data for subjects registered to the study should indicate date ICF was signed, participation in clinical protocol number and title, treatment number, evidence that inclusion/exclusion criteria have been met.

10.1.3.4. Recording of Data on Electronic Case Report Form (eCRF)

No data will be directly entered into the eCRF without source documentation.

The study worksheets provided by the Sponsor may be used to capture all study data not recorded in the subject's medical record. Alternatively, the site may create and use their own study worksheets. Only a subject identification number will be used to identify the subject. The

Investigator must keep a separate log of subject names and medical record numbers (or other personal identifiers).

The protocol will use an Internet-Based Remote Data Entry System, primarily to collect clinical study data at the investigational sites. The system will be used to enter, modify, maintain, archive, retrieve, and transmit data. The system was configured based on requirements from the Sponsor. Paper source documents are to be retained to enable a reconstruction and evaluation of the study. No original observations will be entered directly into the computerized system. Source documents include the clinic or hospital subject files and study worksheets provided by the Sponsor. Data will be recorded in the study worksheets as appropriate to complete and/or clarify source data.

The design of a computerized system complies with all applicable regulatory requirements for record keeping and record retention in clinical studies (21 CFR Part 11 and ICH-GCP; E6) to the same degree of confidence as is provided with paper systems. Clinical Investigators must retain either the original or a copy of all source documents sent to a Sponsor or CRO, including query resolution correspondence. The system is designed so that changes to any record do not obscure the original information. The audit record clearly indicates that a change was made and clearly provides a means to locate and read the prior information. All changes to the data have an electronic audit trail, in accordance with 21 CFR 11.10(e). Electronic signatures will be used in conformance with 21 CFR Part 11.

10.1.3.5. Investigator Site File

All documents required for the conduct of the study as specified in the ICH-GCP guidelines will be maintained by the Investigator in an orderly manner and made available for monitoring and/or auditing by the Sponsor or Sponsor delegate and regulatory agencies.

10.1.3.6. Clinical Study Supplies

The Sponsor or its vendors will be responsible for providing study supplies and for ensuring that they are used, managed and accounted for properly. Accurate and timely records of the disposition and accountability of all investigational products must be maintained by the site and reviewed by the Sponsor representative monitor. The supplies and inventory record must be made available for inspection upon request. Upon completion or termination of the study, the Investigator will keep the remaining clinical supplies along with a copy of the inventory record and a record of the clinical supplies returned. Under no circumstances will the Investigator allow the investigational products to be used other than as directed by this protocol.

Upon completion or termination of the study, all study supplies will be disposed of per instructions from the Sponsor and/or its vendors (CRO).

Clinical study supplies include, however, not limited to: eCRF, study worksheets, laboratory supplies and investigational products.

10.1.4. Data Management

Data Management services will be provided by the CRO. After the data have been entered and verified, various edit checks will be performed for the purpose of ensuring the accuracy, integrity, and validity of the database.

Queries generated from these checks will be sent to the investigational site for resolution, and the database will be updated to reflect query resolutions as appropriate.

For details on data management processes, please refer to the Study Data Management Plan.

10.1.5. Study Completion

This study is expected to end when all required subjects have been enrolled and the last subject has completed the follow-up visit of the study (30 days post last dose of investigational product) and query resolution has been completed. Collection of overall survival data will continue beyond the follow-up visit and will be reported separately from the clinical study report.

10.1.6. Clinical Study Report

A clinical study report will be developed by the Sponsor at completion of data analysis. This report will be a clinical and statistical integrated report, according to the ICH E3 guidelines.

10.1.7. Disclosure

All information provided regarding the study, as well as all information collected/documentated during the study, will be regarded as confidential. The Investigator (or designee) agrees not to disclose such information in any way without prior written permission from the Sponsor.

Any publication of the results, either in part or in total (e.g., articles in journals or newspapers, oral presentations, abstracts) by the Investigator or their representative(s), shall require prior notification and review, within a reasonable time frame, by the Sponsor, and cannot be made in violation of the Sponsor's confidentiality restrictions or to the detriment of the Sponsor's intellectual property rights.

Sponsor will register the study and post study results regardless of outcome on a publicly accessible website in accordance with the applicable laws and regulations.

10.1.8. Records

Data collected at Screening and during the study will be recorded in the subject's source documents and retained at the study site for all subjects who sign informed consent. Subjects who are enrolled in the study will have their data retained in the source documents at the site and also have their data entered into the eCRF. To maintain confidentiality, subjects will be identified only by screening and subject numbers.

The completed eCRFs will be transferred to the Sponsor (or designee). Copies of each source document will be retained by the Investigator (or designee). A compact disk containing the site eCRF data will be provided to the site at the completion of the study. All source documents, records, and reports will be retained by the clinical site in accordance with 21 CFR 312.62(c). The minimum retention time for study records will meet the strictest standard applicable to that site, as dictated by any institutional requirements or local, national, or regional laws or regulations. Prior to proceeding with destruction of records, the Investigator must notify the Sponsor in writing and receive written authorization from the Sponsor to destroy study records.

In addition, the Investigator must notify the Sponsor of any changes in the archival arrangements including but not limited to archival at an offsite facility or transfer of ownership if the Investigator leaves the site.

All primary data, or copies thereof (e.g., laboratory records, eCRFs, data sheets, correspondence, photographs, and computer records), which are a result of the original observations and activities of the study and are necessary for the reconstruction and evaluation of any study report, will be retained in the clinical site archives.

10.1.9. Financing and Insurance

Financing and insurance of this study will be outlined in a separate agreement between CRO and the Sponsor.

10.2. Appendix 2: Clinical Laboratory Tests

- The tests detailed in [Table 9](#) will be performed by the local laboratory.
- All safety laboratories, hematology, chemistry and urine analysis are to be drawn by standard phlebotomy techniques, into the site prescribed appropriate tubes for the specific tests and amounts prescribed by local laboratory, e.g., CBC with differential 5 ml in a purple top tube., chemistry 10 ml in a red top tube. Refer to the laboratory manual for further details on specimen collection and handling procedures.
- Protocol-specific requirements for inclusion or exclusion of subjects are detailed in [Section 5](#) of the protocol.
- Additional tests may be performed at any time during the study as determined necessary by the investigator or required by local regulations.
- Investigators must document their review of each laboratory safety report.

Table 9 Protocol-Required Safety Laboratory Assessments

Hematology	White blood cell count (WBC) with differential (neutrophils, lymphocytes, monocytes, eosinophils, basophils) Red blood cell (RBC) with indices (MCV and MCH) Hematocrit, hemoglobin and platelet count
Serum Chemistry	Glucose, blood Urea Nitrogen (BUN), creatinine, total bilirubin, albumin, aspartate aminotransferase (AST), alanine aminotransferase (ALT), alkaline phosphatase, lactate dehydrogenase (LDH), glucose, and electrolytes (sodium, potassium, chloride, calcium, magnesium, and phosphorus). A direct bilirubin should be obtained if the total bilirubin level is >1.5 times ULN. Creatinine clearance will be done at Screening only.
Lipid panel	triglycerides, total cholesterol, low-density lipoprotein (LDL), and high density lipoprotein (HDL)
Urinalysis (dipstick)	pH, glucose, ketones, protein, specific gravity, bilirubin and evidence of infection; microscopic examination will be done when findings are abnormal.
Other laboratory assessments	Glycated hemoglobin (HbA1c) Thyroid function: Thyroid stimulating hormone (TSH), total T3 and free T4 Coagulation assessment, including prothrombin time (PT), and activated partial thromboplastin time (aPTT). Human chorionic gonadotropin (hCG) pregnancy test (as needed for women of childbearing potential) Follicle-stimulating hormone and estradiol (as needed in women of non-childbearing potential only) Lipase – only for subjects who experience \geq Grade 2 diarrhea

10.3. Appendix 3: Adverse Events: Definitions and Procedures for Recording, Evaluating, Follow-up, and Reporting

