4.3. Justification for Dose

The dose selected for this study (6 mg QW) is based on nonclinical studies, prior clinical studies conducted by BMS (the previous developer) (CA216001, CA216002 and CA216003) and preliminary outcome from the ongoing ACCURACY study conducted by Ayala (NCT03691207). Please also refer to the Investigator's Brochure for further information.

Study CA216001 was a first in human dose escalation study which evaluated doses ranging from 0.4 mg QW to 8.4 mg QW. In the initial dose-escalation, there were no dose limiting toxicities (DLTs) noted in 4 subjects at 6 mg QW. Dose escalation was continued to 8.4 mg QW and DLTs, including a Grade 5 liver failure in one subject, were noted. The case of liver failure was complicated by pre-existing liver injury and possible contribution of an investigational nucleoside analogue, the subject had previously received, known to cause delayed liver toxicity. Consequently, an additional 10 subjects were enrolled at the 6 mg QW dose. There were 4 DLTs observed amongst 4 of these additional subjects including 2 subjects with Grade 3 diarrhea, 1 subject with Grade 3 vomiting/Grade 3 lipase elevation, and 1 subject with Grade 3 large intestinal ulcer with a non-treatment related Grade 3 infectious colitis. Based on this data, the previous sponsor assessed the RP2D as 4 mg QW.

However, upon careful review of these data, Ayala concluded that, with proper control of diarrhea, 2 of the DLTs which were noted at 6 mg QW could probably have been controlled so that they were potentially not DLTs. Importantly this is further substantiated by the observation in the ongoing ACCURACY study that (AL-ACC-01), with proactive control of diarrhea, there was only a 3% (2/34) incidence of Grade 3 diarrhea as opposed to the 19% (8/43) incidence noted in CA216001. The proactive control of diarrhea is delineated below and includes frequent and early use of loperamide followed by a low threshold to use steroids.

Furthermore, study CA216002 evaluated subjects with T-ALL/T-LL at the 6 mg QW dose. The subjects in this study tolerated the 6 mg QW dose well with no reported DLTs.

From a mechanistic perspective interest in using the higher dose of AL101 is driven by PK and pharmacodynamic (PD) results from the Phase 1 Study CA216001 indicate that AL101 exposure (C_{max} and area under the curve [AUC]) increases with approximately linear kinetics for QW

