Grade 3 diarrhea	
Guidelines for the management of diarrhea:
 
 Evaluate subject carefully including laboratory assessments (chemistry, liver function tests and lipase) Loperamide 4 mg at the first onset of diarrhea, then 2 mg every 2 hours around-the-clock until diarrhea free for at least 12 hours. Subjects may take loperamide 4 mg every 4 hours during the night. These doses should not be used for more than 48 hours due to the risk of paralytic ileus. For subjects that cannot tolerate loperamide or do not get adequate relief with maximum doses, standard doses of LOMOTIL® 	
Guidelines for the management of diarrhea:
 
 Evaluate subject carefully including laboratory assessments (chemistry, liver function tests and lipase) Loperamide 4 mg at the first onset of diarrhea, then 2 mg every 2 hours around-the-clock until diarrhea free for at least 12 hours. Subjects may take loperamide 4 mg every 4 hours during the night. These doses should not be used for more than 48 hours due to the risk of paralytic ileus. For subjects that cannot tolerate loperamide or do not get adequate relief with maximum doses, standard doses of LOMOTIL®

Dose Modification Criteria for AL101 -Related Adverse Events	AL101 modification at next dose	
	Dose 6 mg QW	Dose 4 mg QW

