9.3. Statistical Analyses

The statistical analysis plan (SAP) will be finalized prior to database lock and it will include a more technical and detailed description of the statistical analyses described in this section. This section is a summary of the planned statistical analyses of the most important endpoints including primary and key secondary endpoints.

The standard summary statistics for continuous variables are sample size (n), mean, standard deviation, median, minimum and maximum. The standard summary statistics for categorical variables are frequencies and percentages. Time to event variables will be summarized using the Kaplan-Meier method. Where confidence limits are appropriate, the confidence level will be 95% (two-sided), unless otherwise stated. The only test of statistical significance will be performed according to the pre-defined analysis of the Simon two-stage optimal design.

Individual data (including relevant derived variables) will be presented by parameter in listings. Results of statistical analyses, descriptive summary statistics and supportive listings will also be presented.

Baseline values are defined as the last valid value prior to IP administration. Baseline safety data will be presented along with subsequent safety values assessed during or after drug administration.

Detailed methodology for summary and statistical analyses of the data collected in this study will be documented in a statistical analysis plan (SAP), which will be maintained by the Sponsor. This document may modify the plans outlined in the protocol; however, any major modifications will also be reflected in a protocol amendment.

Statistical analyses will be performed using SAS® v9.4 or higher (SAS Institute, Cary NC, USA).

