9.3.4. Safety and Tolerability Analysis

All safety analyses will be made on the Safety Analysis population.

The safety assessment will be based on the frequency of AEs, the incidence of clinically significant abnormalities of laboratory values, concomitant medication use, vital signs, pain assessment and physical examination data.

Adverse events: The AE verbatim descriptions (investigator terms from the eCRF) will be classified into standardized medical terminology using the Medical Dictionary for Regulatory Activities (MedDRA). AEs will be considered treatment-emergent if they start on or any time after the first dose of IP until 30 days after the last dose of IP. The incidence of treatment-emergent AEs will be summarized overall, by system organ class and preferred terms, and by severity grade and relationship to IP. SAEs and AEs leading to discontinuation will also be tabulated.

Other safety data: These data will be summarized by presenting the proportions of subjects with clinically significant abnormalities or by changes from baseline values. Laboratory parameters will be categorized according to CTCAE v5.0 grade and shifts from baseline CTCAE grade to worst postbaseline grade will be summarized using shift tables. Percentages will be based on the number of subjects with baseline and at least 1 post baseline assessment. Laboratory data will be listed, and abnormal results will be flagged.

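### No baseline lipase is required and on-treatment lipase is triggered only by Grade 2 or higher diarrhea, so the planned shift summary has no evaluable subject for lipase on the required schedule

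*Combined protocol and SAP*

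**What the plan says.** **Measurement.** Table 9 (Section 10.2, protocol-required safety laboratory tests) places lipase under other assessments, required "only for subjects who experience" diarrhea of Grade 2 or above. The serum chemistry row, which includes "alkaline phosphatase, lactate dehydrogenase (LDH), glucose, and electrolytes", does not contain it, and the Schedule of Activities has no lipase row at any visit. Table 3 (Section 6.4) asks for lipase within the work-up in the Grade 2, 3 and 4 diarrhea rows. Section 10.2 also states: "Additional tests may be performed at any time during the study as determined necessary by the investigator or required by local regulations".

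**Analysis.** Section 9.3.4 says that laboratory parameters will be graded by CTCAE and that "shifts from baseline CTCAE grade to worst postbaseline grade will be summarized using shift tables". It adds: "Percentages will be based on the number of subjects with baseline and at least 1 post baseline assessment". Section 9.3 defines the starting point: "Baseline values are defined as the last valid value prior to IP administration".

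**Prior signal.** Section 4.3 lists the DLTs among the 10 subjects added at 6 mg weekly in the first-in-human study (CA216001). Two subjects had Grade 3 diarrhea, one had a large intestinal ulcer, and the remaining entry reads "1 subject with Grade 3 vomiting/Grade 3 lipase elevation".

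**The concern.** The analysis section needs a pre-dose and a post-dose value for each laboratory parameter. The testing schedule supplies no pre-dose lipase, and it supplies a post-dose one only in subjects selected by a different toxicity. Three things follow.

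- A lipase shift cannot be tabulated from required data.
- An elevation found during a diarrhea work-up has no comparator, so it cannot be separated from one that was there at entry.
- A proportion computed from the available values describes subjects with Grade 2 or higher diarrhea, not the safety population. The plan does not say so.

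Clinically significant laboratory abnormalities are a secondary safety endpoint (Section 3), and the protocol's own dose justification names lipase elevation among the DLTs at the study's starting dose. That event is recorded with vomiting, which does not trigger a lipase test in this plan.

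**Working it through.** **1. Reproduce the plan's DLT count.** Section 4.3 gives 4 DLTs in 4 of the 10 added subjects. The components are 2 (diarrhea) + 1 (vomiting/lipase) + 1 (large intestinal ulcer) = 4, which agrees. The lipase subject is therefore a different person from the two listed with diarrhea DLTs.

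**2. Count evaluable subjects for a lipase shift.** Under 9.3.4, evaluable n = subjects with a baseline lipase and at least one post-baseline lipase.

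- Required baseline lipase: 0 subjects (no lipase in the Schedule of Activities or the chemistry row).
- Required post-baseline lipase: N × g, where N is the number treated and g the proportion with Grade 2 or higher diarrhea.
- Evaluable n cannot exceed the smaller count, so it is 0 for any g, with N = 67 (6 mg throughout) or N = 73 (67 at 4 mg plus the 6 lead-in subjects).

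**3. What a baseline value alone would change.** The documents do not give g for this study, so the following values are assumptions. N = 67, and every triggered test is assumed to be done.

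| Assumed g | Post-baseline lipase, 67 × g | Evaluable as written | Evaluable with a baseline for all |
|---|---|---|---|
| 30% | 20.1, about 20 | 0 | about 20 |
| 50% | 33.5, about 34 | 0 | about 34 |
| 70% | 46.9, about 47 | 0 | about 47 |

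A baseline makes the triggered values interpretable. It does not turn them into a whole-population incidence, because the remaining subjects still have no required post-baseline lipase.

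**4. Size of the prior signal.** Exact (Clopper-Pearson) 95% limits for one event in n: the lower limit is 1 − 0.975^(1/n), and the upper limit is the p that solves (1 − p)^n + n·p·(1 − p)^(n−1) = 0.025.

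- Added subjects, n = 10: 1/10 = 10%; limits 0.3% and 44.5%.
- All subjects at 6 mg weekly in that study, n = 4 + 10 = 14: 1/14 = 7.1%; limits 0.2% and 33.9%.

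The event is documented, but its rate is almost unknown.

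**5. Set the trigger beside the signal.** The Table 9 trigger is diarrhea of Grade 2 or higher. The Section 4.3 event is vomiting with lipase elevation, and Section 4.3 does not say whether that subject also had diarrhea. A required test would reach such a subject only if Grade 2 or higher diarrhea was present too. Otherwise it depends on the investigator choosing to order lipase.

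**The case against.** The best defence is that lipase here is a reflex test, not a monitored parameter. The amendment summary says it was added for subjects with Grade 2 or higher diarrhea at a competent authority's request. Section 9.3.4 does not name lipase. Other Table 9 tests are also conditional or done once (direct bilirubin, creatinine clearance, FSH and estradiol) and would not fill a shift table either. Section 9.3.4 also allows proportions with clinically significant abnormalities, which need no baseline, and it leaves detail to a later SAP. All of this is fair. It limits the point to lipase and leaves the other shift tables untouched. It does not supply a comparator for the triggered values, and it does not say that their denominator is the subjects tested. Unlike those other tests, lipase is tied to a DLT in the protocol's own dose justification.

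A reader might infer three stronger things that the documents do not support.

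- *That the cited lipase DLT would have been missed.* Section 10.2 lets the investigator order extra tests at any time, and Section 4.3 does not exclude concurrent Grade 2 diarrhea. Detection was not required, which is different from impossible. A discretionary pre-dose lipase would likewise count as a baseline.
- *That Table 3 could not be applied to such a subject.* Grade 3 vomiting, if judged related, falls by itself under the row for other related Grade 3 nonhematologic events. Only an isolated lipase rise would escape, and the documents report no such case.
- *That about 5 to 7 of 67 subjects would have the event.* This is 67 × 1/14 = 4.8 to 67 × 1/10 = 6.7, from a single event. The matching limits are 0.1 to 22.7 and 0.2 to 29.8 subjects. Section 4.3 also reports no DLTs at 6 mg weekly in the T-ALL/T-LL study. The projection carries no useful information.

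Routine on-treatment lipase is also not a free improvement. Asymptomatic Grade 3 values judged related could engage Table 3 and count in the lead-in dose decision.

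**Conclusion.** The point holds for lipase, on the required schedule. No baseline is required, so the shift summary in 9.3.4 has 0 evaluable subjects for this analyte, whatever the diarrhea rate and whether 67 or 73 are treated. A triggered elevation cannot be distinguished from a pre-existing one, and any lipase rate is conditional on Grade 2 or higher diarrhea. The diarrhea-only trigger also sits uneasily with the lipase DLT in Section 4.3, which is listed apart from the diarrhea DLTs (1 of 10; 95% CI 0.3% to 44.5%).

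The count of 0 assumes that no site draws a discretionary lipase before dosing. A few such values would give a small, unsystematic denominator and would not remove the problem. No efficacy result or other laboratory summary is affected. This is a modest gap that is cheap to close.

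**What to change.** 1. **Section 10.2 and the Schedule of Activities:** add lipase to the chemistry sample already drawn at Screening/C1D1 before the first infusion, so that diarrhea-triggered values have a baseline. Keep the triggered test.
2. **Section 9.3.4 (and the SAP):** state that post-baseline lipase is summarised only among subjects tested, with the number tested and the reason for testing shown. State also that no lipase incidence is given for the whole safety population and that any shift applies to tested subjects with a baseline.
3. **Reconcile Table 9 with Section 4.3:** ask the sponsor to explain why diarrhea alone triggers lipase when the cited lipase DLT is listed with vomiting. Whether to test lipase routinely on treatment is the sponsor's clinical decision.

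The cost is one more analyte at the local laboratory on blood already being taken, review of some incidental baseline elevations, and a few lines of text. No visit is added, and sample size and the efficacy analysis do not change.
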